2 STUDY RATIONALE

Reports concerning for direct or indirect healthcare-associated NTM transmission continue to appear in the literature.⁸⁻¹⁰ A *standardized approach* to investigation of healthcare-associated

NTM acquisition in CF patients *is critical to prevention*. Collecting data on potential healthcare-associated transmission events in a systematic, uniform format will increase the likelihood of being able to create a statistical model to predict instances of increased probability of transmission events. Understanding risk for NTM transmission in the setting of the current IP&C guidelines has the potential to *significantly decrease risk of healthcare-associated transmission events of NTM among people with CF*.

An overview of the HALT NTM investigation process is outlined (**Figure 4**). NJH IRB approval for the HALT NTM toolkit is active. Currently the CO-RDP receives CF NTM respiratory samples from across the country and performs culture and WGS analysis. Submitting physicians receive a letter acknowledging receipt of the sample; most commonly informing them that the isolate is genetically unique. However, samples initially identified as unique may subsequently be identified as part of a cluster of highly similar isolates when additional strains are added to the database. We will continue to update the Care Centers on the status of their isolates periodically. When WGS related clusters are identified, we will determine if the patients receive care in the same CF Program.

[figure not shown]

Figure 4: HALT NTM Study Flowchart.

When highly similar isolates are identified within an individual Care Center, a form letter entitled, CO-RDP NTM Isolate Results for CF Care Centers (**Appendix 1**), will be sent to each affected institution. The letter informs the Centers of highly similar NTM isolates among two or more patients within their Center. The letter will also extend the invitation to participate in the HALT NTM study. To put the study in context, we will provide a summary of cluster data available to date, the goals and methods of this study, as well as IRB documents. The invitation to participate in HALT NTM will initiate a simple enrollment process and recommend collaboration with the Center’s local IP&C team for investigation into a potential healthcare-associated transmission event. With enrollment, instructions will be provided on how to access the web-based HALT NTM investigation toolkit to facilitate a standardized healthcare-associated NTM investigation and a HALT NTM Toolkit User’s Guide will be provided (**Appendix 2**).

The primary function of the HALT NTM abstraction toolkit is to assess an occurrence of overlap between two or more patients identified in the cluster within the CF healthcare setting, defined as CF clinic, hospital and research settings. An overlap is defined as a healthcare setting where two or more CF patients identified in the cluster received care in the same setting for any period of time **within 24 hours**. A point instance of overlap is defined as a specific physical room within the healthcare setting (clinic, hospital, or research area) where two or more CF patients identified in the cluster received care. An example includes the following: Subject 1 and Subject 2 are both seen in clinic on 12/12/16. Subject 1 is in the clinic from 10:00-12:00. Subject 2 is in clinic from 1:00-3:00. In this example, an overlap in clinic is observed between Subject 1 and Subject 2 because two clustered patients attended the same CF clinic on the same day. During this example visit, Subject 1 performs spirometry in PFT laboratory Room 1 at 10:00 on 12/12/16 and Subject 2 performs spirometry in PFT laboratory Room 1 at 2:00 on 12/12/16. In this example, a point instance overlap is observed in the PFT laboratory because two clustered patients were in Room 1 in the PFT laboratory on the same day. Because potential transmission events can be direct or indirect, an overlap does not have to occur at the exact same time on a given day. Additionally, subjects may be observed to have an overlap, but a point instance of overlap may not be identified. In either case, data will be recorded accordingly.

Testing for water biofilm sources in the CF healthcare setting: NTM are known to colonize municipal water systems and have been identified in healthcare facilities.²⁷⁻²⁹ NTM are found in free flowing water as well as biofilms on water supply system pipes and both have been implicated in nosocomial outbreaks of infection.³⁰ Modes of acquisition and transmission of NTM among CF patients remains unclear. A multicenter prevalence study of NTM in 2003 did not implicate nosocomial transmission among CF patients, and molecular analysis at that time revealed almost all patients had unique NTM strains.³¹ A more recent study described a biphasic nosocomial outbreak of MAB linked to hospital tap water.³² The authors attributed the first phase of the outbreak of respiratory MAB to routine care practices using hospital tap water with exposure to the aerodigestive tract in high-risk patients. The second phase outbreak occurred among cardiac surgery patients with invasive MAB infections and was attributed to contaminated heater-cooler units of cardiopulmonary bypass machines. Others have implicated inhalation of aerosolized NTM via showerheads as a possible source of acquisition of infection.³³ A recent study demonstrated that showerheads receiving water from municipal water treatment plants **harbor clinically-relevant NTM**.³⁴ On a more global level, Bryant *et al.* reported widespread dominant circulating NTM clones.¹¹ This worldwide distribution could be explained by **prevalent environmental genotypes**. Further environmental evaluation of healthcare environments is essential to understanding healthcare-associated environmental risk factors in **acquisition of NTM infection**.

Biofilms are the preferred samples for isolation of NTM in water systems of all types because the hydrophobic NTM cells preferentially adhere to pipe surfaces where they form biofilms, thus ensuring their persistence. Average colony counts/cm² of premise plumbing biofilm samples is between 1,000-15,000 CFU/cm², whereas water (suspended) densities are between 10-100 CFU/mL.³⁵ Thus, the sensitivity of NTM detection is **orders of magnitude higher for biofilm** compared to water samples. With advanced molecular analysis and better understanding of previous NTM nosocomial outbreaks, the CO-RDP findings of highly related NTM clusters among CF patients within the same CF Care Centers **raises concern for nosocomial**

transmission. In order to better understand risk for nosocomial NTM acquisition among CF patients with clonal NTM respiratory isolates, ***determining the relatedness of clustered CF NTM clinical respiratory isolates to environmental water sources in the CF healthcare setting is imperative.***

2.1 Risk / Benefit Assessment

As a retrospective, epidemiologic study there is no anticipated direct benefit to participants. There is minimal risk to subjects in the study.

3 STUDY OBJECTIVES

3.1 Primary Objective

PART A / Epidemiologic Investigation:

The primary objective of the epidemiologic investigation is to facilitate implementation of a stepwise process by which individual Centers perform retrospective epidemiologic evaluation of patients identified by the CO-RDP as part of an NTM cluster.

PART B / Water Biofilm Collection:

The primary objective of water biofilm collection is to determine if NTM strains identified in clusters are related to the strains isolated from water biofilm sources in the CF healthcare setting.

3.2 Secondary Objectives

PART A / Epidemiologic Investigation:

The secondary objectives are to:

- Determine subject overlap:
Frequency, location and source of overlap within the healthcare system within the 2-year abstraction timeframe.
- Evaluate infection prevention and control (IP&C) measures:
Use of single patient rooms, healthcare staff gowning and gloving, patients wearing masks, aggressive cleaning procedures between patients, and maintenance of patient-to-patient separation of 6 feet or more within the 2-year abstraction timeframe.

PART B / Water Biofilm Collection:

The secondary objectives are to:

- Culture healthcare-associated water biofilm environmental NTM.
- Evaluate effectiveness of a standardized NTM disease treatment protocol to serve as baseline/reference estimates of endpoints in clinical care and future therapeutic trials.
- Support biomarker development for markers of NTM treatment response through banking of clinical specimens and NTM isolates linked with outcomes data.
- Characterize clinical features of patients achieving treatment success compared to those unresponsive to treatment.

4 STUDY DESIGN

4.1 Study Overview

PART A / Epidemiologic Investigation:

This study will retrospectively review and collect data from patients with CF and culture positive for an NTM isolate falling in a highly-related cluster, identified by the CO-RDP, within a single CF Care Center. Two control subjects will be identified by the CO-RDP for every subject falling within a cluster. Retrospective epidemiologic data collection and input into REDCap is detailed (**Appendix 1 and 2**). Up to 20 Care Centers will be offered enrollment.

PART B / Water Biofilm Collection:

This study will also collect and analyze water biofilms from a variety of water sources in the healthcare setting including sink faucets, showerheads, shower hoses, ice machines, drinking fountains, and decorative water features. Environmental sampling instructions are detailed (**Appendix 3**).

5 CRITERIA FOR EVALUATION

5.1 Primary Endpoint

PART A / Epidemiologic Investigation:

Identification of a shared healthcare-associated source(s) between patients in a Care Center with identical NTM isolates.

PART B / Water Biofilm Collection:

Identification of clinically-relevant NTM isolates and prevalent environmental genotypes with in healthcare setting water biofilms.

5.2 Secondary Endpoints

PART A / Epidemiologic Investigation:

The secondary endpoints are:

- Adherence to CF IP&C guidelines.
- Characterization of points of patient overlap.

PART B / Water Biofilm Collection:

The secondary endpoints are:

- Incidence and prevalence of NTM species/subspecies within healthcare water biofilms.
- Determine if biofilm isolates are highly related to isolates recovered from patients.

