
PRIMARY OBJECTIVE
	
PART A / Epidemiologic Investigation: Our primary objective is to implement a standardized epidemiologic investigation, via the HALT NTM tool kit, in CF Care Centers identified as having clusters of highly similar NTM isolates. We will assess the origins and prevalence of healthcare associated patient to patient transmission of NTM among different CF Care Centers. We will characterize the source(s) of direct or indirect patient-to-patient transmission of NTM within an individual CF healthcare setting.
 
PART B / Water Biofilm Collection: The primary objective is to determine if NTM strains identified in clusters are related to strains isolated from water biofilm sources in the CF healthcare setting. Because hospital and clinic plumbing sources could pose a risk to CF patients, we aim to perform WGS of NTM isolates from healthcare biofilms obtained from CF Centers with NTM clusters among patients to determine if the biofilm isolates are highly related to the isolates recovered from patients.

SECONDARY OBJECTIVES
	
PART A / Epidemiologic Investigation: The secondary objectives are to:
 
 ▪ Assess degree of proximity of subjects in time and/or space. ▪ Compare the relationship between similarity of strains and degree of proximity of subjects. ▪ Model the relationship between the degree of similarity and strains with the proximity and subject characteristic variables. 
PART B / Water Biofilm Collection:

	
The secondary objectives are to:
 
 ▪ Characterize clinically-relevant NTM isolates and healthcare biofilms. ▪ Describe most common biofilm sources within the healthcare setting harboring clinically relevant NTM isolates.
NUMBER OF PARTICIPANTS	
PART A / Epidemiologic Investigation: Unlimited and based on the number of patients identified in an NTM cluster within an individual CF Care Center (prospectively collected data). Two controls will be identified for every subject within a cluster.
 
PART B / Water Biofilm Collection: N/A

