PARTICIPANT SELECTION CRITERIA: Inclusion Criteria	
PART A / Epidemiologic Investigation: Inclusion Criteria:
 
 1. Written informed consent is not required for this retrospective epidemiological study. 2. Diagnosis of CF consistent with the 2017 CFF guidelines. 3. Male or female participant of any age who have a history of NTM species or sub-species collected from expectorated sputum, induced sputum and/or bronchoalveolar lavage and identified by the CO-RDP as falling into a highly-related cluster within a single CF Care Center. 4. Controls subjects are male or female participants of any age who have a history of NTM species or sub-species collected from expectorated sputum, induced sputum and/or bronchoalveolar lavage and identified by the CO-RDP as NOT falling into a highly-related cluster within a single CF Care Center. 
PART B / Water Biofilm Collection: Inclusion Criteria: N/A

PARTICIPANT SELECTION CRITERIA: Exclusion Criteria	
PART A / Epidemiologic Investigation: N/A
 
PART B / Water Biofilm Collection: N/A

CONCOMITANT MEDICATIONS	
Allowed: N/A Prohibited: N/A

PRIMARY ENDPOINT	
PART A / Epidemiologic Investigation: Identification of a shared healthcare-associated source(s) between patients in a CF Care Center.
 
PART B / Water Biofilm Collection:

	Identification of biofilm isolates that are highly related to the isolates recovered from patients.
SECONDARY ENDPOINTS	
PART A / Epidemiologic Investigation: The secondary endpoints are:
 
 ▪ Incidence and prevalence of CF NTM species/subspecies by geographical region. 
PART B/ Water Biofilm Collection: The secondary endpoints are:
 
 ▪ Incidence and prevalence of healthcare-associated water biofilm NTM species/subspecies by geographical region.
EXPLORATORY EVALUATIONS	None
PLANNED INTERIM ANALYSIS	No formal interim analysis involving a data monitoring committee (DMC) is planned.

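### The synopsis and Sections 5.2/15.4 give different secondary endpoints, and incidence and regional prevalence cannot be formed from the patients and swabbing described

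*Protocol*

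**What the plan says.** **Synopsis, Secondary Endpoints.** Each part has one item. Part A: "Incidence and prevalence of CF NTM species/subspecies by geographical region". Part B: "Incidence and prevalence of healthcare-associated water biofilm NTM species/subspecies by geographical region".

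**Section 5.2.** Part A has two items: "Adherence to CF IP&C guidelines" and "Characterization of points of patient overlap". Part B has two: "Incidence and prevalence of NTM species/subspecies within healthcare water biofilms" and "Determine if biofilm isolates are highly related to isolates recovered from patients".

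**Section 15.4.** The analysis text follows 5.2. It covers adherence and overlap for Part A. For Part B it covers incidence and prevalence in biofilms without region, plus comparisons with related patient isolates.

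**Synopsis, Primary Endpoint, Part B.** "Identification of biofilm isolates that are highly related to the isolates recovered from patients".

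**Who and what is sampled.** In the synopsis selection criteria, cases have a history of NTM and belong to a cluster within one Center; controls also have a history of NTM but do not belong to such a cluster. Section 4.1 sets two controls per case. Section 15.1.1 bases all analyses on the clustered subjects. Under the synopsis heading on study duration, Centers become eligible in both parts when a cluster is found, and Section 15.6 caps them at 20. The synopsis primary objective for Part B refers to "healthcare biofilms obtained from CF Centers with NTM clusters among patients". Appendix 3 describes swab technique by outlet type.

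**The concern.** There are two problems. First, current sections of the same protocol disagree on what the secondary endpoints are, and on whether relatedness of biofilm and patient isolates is primary or secondary. Second, some of the named quantities need a denominator or a time base that the described sampling does not provide.

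If the plan is followed as written, one of two things happens. Either the Part A endpoint declared in the synopsis is silently dropped, since Section 15.4 contains no analysis of it. Or a one-time proportion from Centers chosen for having clusters is reported as incidence, or as the epidemiology of a region. Infection-control readers could then take a figure from selected Centers for a regional rate.

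**Working it through.** The protocol states no sample size or precision for these endpoints, so there is no planned figure to reproduce. The check compares the texts and then asks what each quantity needs.

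**Step 1. The lists side by side.**

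| Item | Synopsis | Section 5.2 | Section 15.4 |
|---|---|---|---|
| A: regional incidence and prevalence in patients | secondary | absent | absent |
| A: guideline adherence | absent | secondary | secondary |
| A: points of overlap | not an endpoint | secondary | secondary |
| B: incidence and prevalence in biofilms | secondary, by region | secondary, no region | secondary, no region |
| B: biofilm-patient relatedness | **primary** | **secondary** | comparisons listed as secondary |

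Part A has no item in common between synopsis and body. Part B shares one, with different scope. On relatedness, Section 15.3 sides with the synopsis by including it in the primary analysis, while the Part B primary endpoint in Section 5.1 does not mention it. The body therefore does not settle its rank either.

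**Step 2. Part A denominator.** Prevalence is the number of positive patients divided by the number of patients in the population. Incidence is the number of new positives divided by time at risk among patients who start negative.

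- Registry figure in Section 1: 1,903 / 15,041 = 0.1265, which agrees with the stated 12.7%. Its denominator is patients cultured that year.
- Study sample with *n* clustered subjects and 2*n* controls, all with a history of NTM: 3*n* / 3*n* = 100% positive. Under Section 15.1.1, clustered subjects only: *n* / *n* = 100%.
- No patient without NTM is enrolled, so nobody in the sample is at risk of a first positive culture.

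The share of clustered patients is likewise set by the design. It is *n* / 3*n* = 33.3% with controls, or 100% under Section 15.1.1. In the preliminary data of Section 1.2, 12 / 114 = 10.5% (stated as 11%) were clustered within the same Center. The ratios are 33.3 / 10.5 = about 3.2 and 100 / 10.5 = about 9.5. The 114 relate to one subspecies only, so this is context and not a benchmark. It shows that shares in the enrolled sample do not estimate a population quantity.

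**Step 3. Part B incidence.** An incidence for outlets needs outlets found negative, a later sample of the same outlets, and the time between. Appendix 3 gives no second round, interval or number of outlets. With the one swabbing it describes, observed changes from negative to positive are 0 and observed time at risk is 0, so no rate can be formed. What can be formed is *x* / *m*, the number of outlets yielding a species over the number of outlets sampled.

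**Step 4. Region.** No regions are defined. Centers enter because a cluster was found, so even a correct proportion describes cluster Centers and not the region they lie in. This applies to the synopsis wording; the Part B line in 5.2 carries no region.

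**The case against.** The strongest reply has four parts.

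*These are descriptive endpoints.* No test or sample size rests on them, and overlap is close to the proximity objectives in the synopsis. This is true and limits the severity. It does not remove the contradiction: adherence appears nowhere in the synopsis objectives or endpoints, and the rank of relatedness concerns a primary endpoint.

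*Appendix 3 is technique and not a schedule.* A reader might infer that it rules out any return to an outlet. It does not. It tells the sampler to come back if a faucet or spigot is wet, it is silent on rounds, and the study runs for 3 years. What stands is that no repeat round or time base is specified; the wet-outlet return is not follow-up.

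*Wider sources exist.* The protocol describes a national isolate bank, registry culture counts, registry identifiers and zip codes. A reader might infer that regional prevalence could never be obtained. The documents do not support that. However, none of these sources is named for this endpoint, and Section 15.1.1 confines analyses to clustered subjects.

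*The Section 5.2 line is partly sound.* A reader might infer that it fails altogether. It does not: its prevalence element can be read as the proportion of sampled outlets that are positive in enrolled Centers. Only its incidence element lacks support.

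A reader might also wish to size the problem as precision lost to correlation between outlets within a Center. That would need assumed numbers of regions and outlets and an assumed correlation, and it would arise even with randomly chosen Centers. It does not measure this defect.

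**Conclusion.** The point holds. The synopsis and Sections 5.2/15.4 contradict each other: no common Part A endpoint, a regional scope for Part B in one place only, and two ranks for relatedness. A statistical analysis plan cannot decide which protocol list governs.

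From the enrolled sample, Part A incidence and regional prevalence cannot be estimated, because NTM positivity is 100% by selection and Centers are chosen for having clusters. From the sampling described, biofilm incidence cannot be formed; a proportion of sampled outlets can.

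The Part A conclusion rests on the selection criteria and analysis set as written, and on no external source being named. The Part B conclusion rests on there being no sampling schedule beyond Appendix 3; a specified second round with dates would change it. The consequence is mislabelled or dropped secondary results, and uncertainty over one Part B primary endpoint. It does not invalidate the study.

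**What to change.** 1. Use one endpoint list throughout. Put the Section 5.2/15.4 Part A endpoints (adherence and overlap) in the synopsis; they match the Part A objectives in Section 3.2.
2. State once whether biofilm-patient relatedness is primary or secondary, and align the synopsis with Sections 5.1, 5.2, 15.3 and 15.4.
3. Delete *incidence* and the regional breakdown. For Part A the alternative is to keep a regional measure and name an external source with its denominator, with a matching exception in Section 15.1.1.
4. Restate the Part B endpoint as the proportion of sampled outlets yielding each species or subspecies, by outlet type, in enrolled cluster Centers, with intervals that allow for clustering by Center. This also serves the synopsis objective of describing which sources most often harbor relevant NTM.

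The cost is protocol wording. The claims become narrower: the results describe enrolled Centers at the time of sampling, and not rates over time or conditions in a region.

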6 PARTICIPANT SELECTION

6.1 Study Population

Participants with a diagnosis of CF who meet all of the inclusion and none of the exclusion criteria will be eligible for participation in this study.

6.2 Inclusion Criteria

PART A / Epidemiologic Investigation:

1. Male or female participant of any age at enrollment Diagnosis of CF consistent with the 2017 CFF Guidelines.
2. NTM-positive for a **species or sub-species** in the 2 years prior to enrollment that has never been treated or current Denver single-center study participant.

PART B / Water Biofilm Collection:

N/A

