
In this study, we are unable to exclude NTM acquisition from direct patient-to-patient contact or via a common environmental source outside the healthcare setting. Evaluation of non-healthcare settings is beyond the scope of this project, but serves as a potential future area of investigation. There may also be a baseline frequency of patient overlap that is not related to transmission events in the healthcare setting that we expect to capture with evaluation of control pairs of subjects. Despite this small sample size, this preliminary data provides insight into the frequency and nature of patient overlap in the healthcare setting and reveals that among CF patients receiving healthcare in the same location, there are opportunities for close direct or indirect contact. In the setting of strict IP&C measures with single patient rooms, healthcare staff gowning and gloving, patients wearing masks, aggressive cleaning procedures between patients, and maintenance of patient-to-patient separation of 6 feet or more, direct and indirect patient overlap should be minimized. However, incidental or unanticipated contacts remain a risk. If patients in fact have no direct or indirect contact, *investigation of the healthcare environment is essential to eliminate a common healthcare-associated environmental source as the point of CF patient NTM acquisition*.

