15.1.1 Data Sets Analyzed

All analyses will be based on the group of subjects that are identified by the CO-RDP as having NTM isolates, defined as highly similar strains at the genomic level, harbored by two or more patients within a single Care Center.

152 Demographic and Baseline Characteristics

The following baseline demographic and clinical characteristics will be reported: age, gender, race, ethnicity, zip code, and NTM sub/species.

153 Analysis of Primary Endpoint

PART A / Epidemiologic Investigation:

The primary endpoint will characterize the origins and prevalence of healthcare-associated patient-to-patient transmission of NTM among different CF Care Centers. We will further characterize the source(s) of direct or indirect transmission of NTM within an individual CF healthcare setting. We will identify a set of variables used to assess degree of proximity of subjects in time and/or space. For example, two subjects with neighboring rooms at a hospital would have close proximity, but proximity would be increased for two subjects at a facility that had longer overlap time, relative to a pair of subjects that had shorter overlap. We will explore creating composite measures of quantitative proximity that incorporate multiple variables. Qualitative measures of proximity, such as location type (testing laboratory, patient room) will also be assessed. Several testing approaches will be used to compare the relationship between similarity of strains and degree of proximity of subjects. In the simplest form, descriptive statistics will be computed for proximity variables, for pairs of subjects who are determined to have similar strains versus those who have dissimilar strains, and multivariate or 2-sample t-tests will be performed to test for differences between these groups. More advanced modeling will be performed to determine the relationship between the degree of similarity in strains with the proximity and subject characteristic variables; multiple linear regression will be used when considering continuous strain similarity, while multiple logistic regression will be used when considering subjects with dichotomized (similar/dissimilar) strains to other subjects.

PART B / Water Biofilm Collection:

The primary endpoint will characterize clinically-relevant NTM found in water biofilms within CF healthcare settings and determine if the biofilm isolates are highly related to isolates recovered from patients.

154 Analysis of Secondary Endpoints

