APPENDIX 2 REDCAP USER GUIDE

So, you've received a letter from National Jewish Health Advanced Diagnostic Laboratories (NJH ADx) saying you have patients at your center with a highly similar strain of NTM. Now what?

1. Contact [name] at NJH. She will help you with initial questions regarding study design and study start-up, including IRB and database requirements.
2. For NJH REDCap access, you will be sent a link to complete REDCap training. You will be asked the following:
 - For the question "Are you an employee of National Jewish Health?" select No.
 - Explain your affiliation as "HALT NTM"
 - National Jewish Health Sponsor is "[name]"
 - For department, indicate your CF center/institution name.
 - Complete the rest as indicated.
 - Email [name] or [name] once you've been given access so you can be added to the project.
3. Now you have access to the database. Log on to REDCap. On the welcome screen, open the HALT NTM project.
4. On the left hand side under Applications, open the File Repository. Download the HALT NTM cheat sheet.
5. Print a HALT NTM cheat sheet for each unique pair:
 - If there are two patients listed on your letter, you will have one unique pair.
 - If there are three patients listed on your letter, you will have three unique pairs.
 - If there are four patients listed on your letter, you will have six unique pairs.
 - This is because the date ranges are compared between two subjects and is unique for each pair.
6. Complete the first six lines on the HALT NTM cheat sheet for each unique pair. You will need to refer to it during pairing and data extraction.
7. Back in REDCap, on the left hand side under Data Collection, click Add / Edit Records. On the Add/Edit Records page, click on the button Add new record. You will be taken to the Record Home Page. There will be a NEW Study ID XXX-XX. Record that number (XXX-XX) on the HALT NTM cheat sheet. It is auto-generated by REDCap. You will need it later.
8. The first Form to complete is Demographics. Open the form by clicking on the circle under Demographics. Near the top of the form under the header **Pairs Survey** is a link to the "**Finding Pairs survey**." Click on the link. You will be taken to an interactive tool that will help you determine if this subject is "subject 1" or "subject 2" in this pairing.

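### Section 6.2 contradicts the synopsis and section 4.1 on who is eligible, and section 15.1.1 leaves the controls out of every analysis

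*Protocol*

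**What the plan says.** The protocol describes the Part A population in four places.

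- **Synopsis, Inclusion Criteria.** Cases are CF patients of any age with a history of NTM, "identified by the CO-RDP as falling into a highly-related cluster within a single CF Care Center". Controls have a history of NTM and are "identified by the CO-RDP as NOT falling into a highly-related cluster within a single CF Care Center".
- **Section 4.1.** The population is defined by cluster membership, and controls are added: "Two control subjects will be identified by the CO-RDP for every subject falling within a cluster".
- **Sections 6.1 and 6.2.** Section 6.1 says that patients "who meet all of the inclusion and none of the exclusion criteria will be eligible for participation in this study". Section 6.2 then lists a CF diagnosis and NTM positivity for a species or subspecies "in the 2 years prior to enrollment that has never been treated or current Denver single-center study participant". It mentions neither clusters nor controls.
- **Section 15.1.1.** "All analyses will be based on the group of subjects that are identified by the CO-RDP as having NTM isolates", which the sentence goes on to define as highly similar strains shared by at least two patients of one Center.

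The discussion within section 1.2 explains what the controls are for. There may be a background level of overlap unrelated to transmission, which "we expect to capture with evaluation of control pairs of subjects".

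**The concern.** There are two conflicts, one on who may enter and one on who is analysed.

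On entry, the synopsis and section 6.2 cannot both be followed. A Center that works from the synopsis takes every cluster member and control with any NTM history. A Center that works from 6.2 would drop those outside the Denver branch who have been treated or have had no positive culture in the last two years. Patients in the pooled analysis could then have been selected by different rules at different Centers.

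On analysis, a control is by definition someone not in a within-Center cluster, while 15.1.1 restricts all analyses to people who are. Read literally, the comparison group that the design recruits is never analysed. The background overlap rate, against which overlap among clustered patients should be judged, then has no assigned data.

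**Working it through.** The protocol gives no computed sample size or power figure to reproduce (section 15.6 states none). The check is a comparison of the texts, followed by a count of pairs.

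**Step 1: the two eligibility lists.**

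| Element | Synopsis | Section 6.2 |
|---|---|---|
| NTM positivity | Any history | Within 2 years before enrollment, or Denver branch |
| Prior NTM treatment | No limit | Never treated, or Denver branch |
| Cluster membership | Required for cases | Not mentioned |
| Controls | Own criterion | Not mentioned |

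Two other sections fit the synopsis rather than 6.2. Section 9.1.5 has sites record whether a subject has had or is having NTM treatment, so treated patients are expected. The abstraction window in the section 1.2 discussion starts two years before the first positive culture of the longest-positive patient. It is anchored on that culture, not on enrollment.

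**Step 2: pairs lost when one member is dropped.** Appendix 2 counts pairs as n(n−1)/2, for example: "If there are three patients listed on your letter, you will have three unique pairs". Dropping one member removes n−1 pairs, a share of (n−1) ÷ [n(n−1)/2] = 2/n.

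| Cluster size n | Pairs | Pairs lost |
|---|---|---|
| 2 | 1 | 1 (100%) |
| 3 | 3 | 2 (67%) |
| 4 | 6 | 3 (50%) |

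**Step 3: scale at one Center.** Section 1.2 reports six clusters of 2 to 3 patients at the preliminary Center. Let a clusters have two patients and 6−a have three, with a from 1 to 5, and assume that no patient is in two clusters.

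- Patients: 2a + 3(6−a) = 18−a, so 13 to 17.
- Within-cluster pairs: a + 3(6−a) = 18−2a, so 8 to 16.
- One exclusion removes 1 or 2 pairs: from 1/16 = 6% to 2/8 = 25% of that Center's pairs.

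This uses the preliminary Center for cluster sizes only. It does not predict how many patients 6.2 would exclude.

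**Step 4: the controls.** At two controls per case, 13 to 17 cases bring 26 to 34 controls, or 2/3 of all subjects. Section 15.1.1 omits all of them.

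**Step 5: effect on the planned comparison.** Section 15.3 compares similar-strain pairs with dissimilar-strain pairs. Take a Center with one cluster of k cases and 2k controls. Assume that the controls are at the same Center and that every pair containing a control is dissimilar. Total pairs are 3k(3k−1)/2.

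| k | Similar/dissimilar, 15.1.1 as written | Similar/dissimilar, controls included |
|---|---|---|
| 2 | 1/0 | 1/14 (15 pairs in all) |
| 3 | 3/0 | 3/33 (36 pairs in all) |
| 4 | 6/0 | 6/60 (66 pairs in all) |

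As written, a single-cluster Center has no dissimilar pairs of its own.

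**The case against.** The strongest reply is that 6.2 is never used as a patient screen. The CO-RDP identifies cases and controls, a letter goes to the Center, and Appendix 2 builds pairs directly from the patients listed there without an eligibility step. Screen failure is marked not applicable. This stands as far as it goes: uncontrolled entry is not the risk, and the loss of listed patients depends on a Center taking 6.2 at its word. But section 6.1 tells it to do so, section 6.4 gives no tolerance, and section 13 ties protocol violations to the eligibility criteria.

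The phrase about never having been treated could also refer to the species or subspecies rather than the patient. That reading is possible and would exclude fewer people, but it still conflicts with a synopsis that sets no treatment limit.

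On the analysis set, the similar-versus-dissimilar comparison in section 15.3 is a natural home for control pairs, and the synopsis promises a control comparison group. Dissimilar pairs would also survive without controls where a Center has several clusters. With the counts in step 3, cross-cluster pairs would number 78−8 = 70 (13 patients) to 136−16 = 120 (17 patients). This is a real limit on the harm. Those pairs, however, are not the control pairs described in section 1.2, and section 15.3 is itself governed by the restriction in 15.1.1 to clustered patients.

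Finally, the size of the selection effect is not demonstrated. That is correct, and none is claimed.

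**Conclusion.** Both contradictions hold in the current text and must be fixed. Section 6.2 sets time, treatment and Denver conditions that the synopsis and section 4.1 do not, and omits the cluster and control criteria that they do set. Section 15.1.1 positively excludes the controls from all analyses, so this is more than a detail left to the SAP.

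Each cluster member dropped under 6.2 costs all, two-thirds or half of the pairs in a cluster of two, three or four. The number who would be dropped is unknown. It could be nil where a Center simply works from its letter, and patients admitted through the Denver branch are unaffected. The omission under 15.1.1 is complete: two of every three planned subjects. The Center-level ranges rest on the preliminary cluster sizes and on no patient being in two clusters. The similar/dissimilar counts rest on same-Center controls whose pairs are all dissimilar.

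**What to change.** 1. **Section 6.2, Part A.** Replace the list with synopsis items 2 to 4: CF diagnosis; cases of any age with a history of NTM and an isolate in a within-Center CO-RDP cluster; controls with a history of NTM and not in such a cluster. Delete the two-year, never-treated and Denver wording. Keep NTM treatment as a recorded characteristic, as section 9.1.5 already provides.
2. **Section 15.1.1.** Define the analysis set as the cluster cases together with their CO-RDP-identified controls, in line with section 4.1.

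The same amendment should say whether controls come from the same Center as their cases and how control pairs are formed, since the steps in Appendix 2 speak only of patients listed in the letter.

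The two core changes are short text corrections. They need no new data and no patients beyond those the synopsis and section 4.1 already admit. As a protocol amendment they require prior written IRB/IEC approval under section 17.1, which is the main practical cost.
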